1. SYNOPSIS

Title:	A Prospective Study to Evaluate the Performance and Operation of the Brevera Breast Biopsy System		
Device(s):	The Hologic Brevera Breast Biopsy System with CorLumina Imaging Technology		
Objective:	To obtain clinical, operational, and performance data and feedback on the Brevera Breast Biopsy System		
Design:	Prospective, multi-center, controlled data collection study		
Primary Outcome:	To obtain data on the operation and feedback from the perspective of the clinician(s), patients, and technologist(s) using the system.		
Planned Enrollment:	Up to 500 subjects		
Population:	Women with suspicious findings on previous imaging (e.g. mammographic, Magnetic Resonance Imaging or Conventional Diagnostic Ultrasound imaging (screening or Diagnostic)) who are sent for biopsy.		
Follow-up Schedule:	No follow-up is required of subjects after the procedure and associated data collection.		
Number of Sites:	Up to 10 across The Netherlands, Italy, France, Germany, Spain and the United Kingdom		
Study Duration (Estimated):	Study Start:Q1/20Enrollment Completion:Q3/20Last Patient, Last Visit:Q3/20Final Report:Q4/20)17)17	
Inclusion Criteria:	 Female aged 18 years of age or older Subject has at least one breast imaging finding requiring biopsy for which images are available Subject is able to understand, read and sign the study specific informed consent form after the nature of the study has been fully explained to her 		

Exclusion Criteria:	 Patients who, based on the physician's judgement, may be at increased risk or develop complications associated with core removal or biopsy. 	
	 Patients receiving anticoagulant therapy or may have bleeding disorders which may put the patient at increased risk of procedural complications based upon physicians judgement 	
Hologic:	Hologic, Inc.	
CRO:	Factory CRO for Medical Devices BV	

2. INTRODUCTION

The Brevera Breast Biopsy System integrates tissue acquisition, real time imaging, and post biopsy handling all during the same procedure. The device will receive CE Mark and be commercially available in all of the countries as part of this protocol before any study procedures are performed. The commercial device will be utilized according to the Instructions for Use.

2.1 Summary of Animal Testing Data

In July 2016, Hologic conducted an animal study titled, "GLP Acute Evaluation of the Brevera Vacuum-Assisted Breast Biopsy System in the Porcine Model."

The objective of this study is to support, using attribute data, that the Gen 2 system adequately performs the following functions using tissue in an animal model:

- 1. Acquire core tissue samples from the biopsy site.
- 2. Transport tissue samples into the filter wheel.
- 3. Capture X-ray images of transported tissue cores in the tissue filter.

The results of this study demonstrate that the device performs to specifications and can be used in human subjects.

2.2 Device Description

The Brevera Breast Biopsy System with CorLumina imaging technology is a vacuum-assisted biopsy device, which is used to remove breast tissue in a minimally invasive manner using stereotactic or tomosynthesis imaging. The system is designed for biopsy and for radiographic image acquisition and display only. The biopsy device will come in contact with tissues and/or body fluids.

[figure not shown]

Figure 1: Brevera Breast Biopsy System with CorLumina Imaging Technology System Overview

The user interface for data entry, patient selection, and image acquisition and review is on the Imaging display. The user interface for controlling the modes of the biopsy device are buttons on the Technologist display and on the remote control device. The user interface for arming and firing the biopsy device is on the remote control device. The user rotates the aperture on the biopsy device with the thumbwheel on the disposable biopsy needle. The user adjusts the size of the aperture on the biopsy device by assembling the introducer in one of two preset positions along the needle shaft.

2.3 Device Accountability

The Hologic operations team will keep records to document the shipment and installation of the commercial system. The Principal Investigator or an authorized designee shall keep records documenting the type, and use of the devices.

2.4 Intended Use/Current Indication for Use

See product specific Instructions for Use.

2.5 Device Procedure(s)/Training

Prior to use in clinical procedures and the implementation in the standard practice, technologists and clinicians will be trained by a Hologic representative on the use of the new device (according to Instructions for Use) and the features. This training will cover quality control procedures as well as didactic training on the equipment. The investigators selected for this study have previous experience with Breast Biopsy Core Sampling.

3. STUDY JUSTIFICATION

The study has been designed to collect data on the operation and to collect feedback from the medical staff and patients on the operation and performance of Brevera Breast Biopsy System with CorLumina imaging technology.

4. THIS STUDY FALLS IN LINE WITH HOLOGIC'S POST MARKET SURVEILLANCE PROGRAM. ACCORDING TO THE REQUIREMENTS AS SET FORTH IN THE ISO 14155, MEDDEV 2.12-1 GUIDELINES ON A MEDICAL DEVICES VIGILANCE SYSTEM, MEDDEV 2.12-2 POST-MARKET CLINICAL FOLLOW-UP STUDIES, AND MEDDEV 2.7-1 CLINICAL EVALUATION, AND AS OUTLINED IN THIS PROTOCOL, THIS POST-MARKET, REGISTRY/OBSERVATIONAL STUDY WILL PROVIDE DATA FOR MEASURING DEVICE PERFORMANCE AND OPERATION IN A REAL WORLD SETTING. THIS POST-MARKET TRIAL IS INTENDED TO EVALUATE THE CLINICAL EVIDENCE THROUGHOUT THE LIFE CYCLE OF OUR PRODUCT, TO PERFORM RISK ASSESSMENT AND TO COLLECT FEEDBACK FROM THE MEDICAL STAFF AND THE PATIENT ON THE OPERATION OF THE BREVERA BREAST BIOPSY SYSTEM WITH CORLUMINA IMAGING TECHNOLOGY. POTENTIAL RISK/BENEFIT

4.1 Potential Clinical Benefit

There are no clinical benefits to the patient as the patient would have the Brevera procedure whether or not they choose to participate in this study or not. Patients will undergo the same standard procedure if they choose not to participate in this study. The results learned from this study could help future patients.

4.2 Anticipated Adverse Device Effect(s)

Common risks associated with the use of any commercial biopsy system are limited to the region surrounding the biopsy site and include:

- Bruising and swelling of the breast
- Infection or bleeding at the biopsy site
- Altered breast appearance, depending on how much tissue is removed and how your breast heals
- Excessive pain following the procedure at the biopsy site

All of the incidents above are related to the biopsy procedure and not necessarily the devices themselves.

4.3 Risk Benefit Rationale

This clinical study is justified because Hologic and clinical investigators believe the potential benefits outweigh the potential risks of study participation. There are no additional risks known for the commercially available devices.

5. STUDY DESIGN

5.1 Study Objective(s)

The objective of this study is to obtain clinical, operational, and performance data and feedback on the Brevera Breast Biopsy System.

5.1.1 Hypotheses

The hypothesis of this study is that the new breast biopsy system could provide:

- 50% Reduction in tissue needed for accurate diagnosis
- 25% Reduction in procedure time
- 50% Reduction in post-biopsy complications
- Weight of grams of tissue per a full 12 chamber
- # of samples needed to provide 1 gram of tissue
- 90% Reduction in discordant biopsies

Reduction in marker dislocation

The current standard of care includes obtaining breast biopsy core samples and verifying the samples using the mammography unit in a room which is next to the room with the biopsy table. With the Brevera procedure, the breast biopsy core samples are obtained, and the system shows images of the samples, providing instant verification.

The data will be compared to data already collected by Hologic, site aggregate data on the current standard of care, and relevant literature (see last page of protocol).

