5.2 Study Design

Prospective, multi-center, controlled data collection study. This study will include collection of breast imaging from the prior exam leading up to the Brevera Breast Biopsy System Procedure.

Surveys have been created in order to obtain information related to feedback from the clinician(s), patient, and technologist(s). The surveys include questions that relate to the overall feel and aesthetic of the product as well at the overall performance of the Brevera biopsy system. The questionnaires will be given to the clinician(s), patient, and the technologist(s) at the conclusion of the procedure and will be focused for each target group. Once a patient has completed the Brevera procedure, her direct participate in the study is concluded. There are no follow-up visits for this data collection.

The surveys will be administered via paper forms to capture the questionnaire data. The results of the survey questions will be compiled and used to support publications.

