5.3.1 Performance Evaluation

- Procedural information
 - Number of core biopsy samples obtained
 - Time at six different points during the Brevera Breast Biopsy System procedure.
 - Data on whether the marker dislocated (>1cm) immediately post deployment.
 - The next steps for the patient (routine screening, diagnostic surgical biopsy, therapeutic surgery, other).
 - Safety assessment include all device and procedure related AEs that occur in the study following treatment to the device.
- Biopsy sample information
 - Whether the lesion has previously been classified as a B3 lesion (uncertain malignancy potential).
- Histology evaluation
 - Histology results of each lesion.
 - Weight of the core biopsy samples obtained for each lesion
- Clinician, Technologist and Patient questionnaire

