5.4 Schedule of Assessment(s)

Clinicians, Patients, and Technologists will be asked about their experience as it directly relates to the procedure that they underwent or performed. Additionally, subjects shall be evaluated from the time of the procedure through their release from the outpatient treatment facility and treated per standard of care for any adverse events which are experienced. Pathology results will be recorded once they become available.

Assessment	Baseline	Procedure
Informed Consent	Х	
Medical History*	Х	
Physical Assessment*	Х	х
Adverse Event Evaluation		Х
Procedure*		х
Questionnaires**		Х

Table 1 - Schedule of Assessments

* Per standard of care

** To be completed by Clinicians, Patients, and Technologists

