5.5 Subjects

This study will recruit up to 500 females 18 years of age or older with suspicious findings on mammographic screening or diagnostic exam who are sent for biopsy.

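### Two hypothesised gains, fewer discordant biopsies and less tissue needed, have no matching item in the protocol's own data list

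*Combined protocol and SAP*

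**What the plan says.** Section 5.1.1 lists the benefits the system could provide. Two of them are "90% Reduction in discordant biopsies" and "50% Reduction in tissue needed for accurate diagnosis". It gives no baseline for either and does not define a discordant biopsy. It then states: "The data will be compared to data already collected by Hologic, site aggregate data on the current standard of care, and relevant literature".

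Section 5.3.1 Performance Evaluation itemises the data. On pathology it lists "Histology results of each lesion". On tissue it lists the core count and "Weight of the core biopsy samples obtained for each lesion". It also lists times at six points, marker dislocation, the patient's next step, related adverse events, prior B3 status and the questionnaires.

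On timing, section 5.2 says "The questionnaires will be given to the clinician(s), patient, and the technologist(s) at the conclusion of the procedure", and section 5.4 says "Pathology results will be recorded once they become available". Section 6 leaves the conduct of the biopsy to the clinician and local standard of care, and collects images from the procedure and from the prior exam. Section 8 plans descriptive tabulation of all variables with 95% confidence intervals.

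**The concern.** A hypothesis about discordance needs a recorded concordant-or-discordant call for each lesion, made by a stated rule. A hypothesis about tissue needed requires some record of when the sample became sufficient. The protocol's list has neither.

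If only the listed data are collected, tabulating them yields no discordance rate. Someone would have to review stored images against histology afterwards, with a definition chosen once results are in hand. The planned comparison with sponsor data, site aggregates and literature could then not be shown to be like for like. A lower core weight could also be read as a saving in tissue needed when it reflects only local sampling habits, with no concordance label to show whether diagnostic adequacy was kept.

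**Working it through.** The protocol derives no figure for either hypothesis, so the main check sets hypotheses beside listed data.

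**Step 1. Hypotheses in section 5.1.1 against items in section 5.3.1 Performance Evaluation**

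| Hypothesis | Listed item | Direct measure? |
|---|---|---|
| Procedure time | Times at six points | Yes |
| Post-biopsy complications | Device- and procedure-related adverse events | Yes |
| Marker dislocation | Dislocation beyond 1 cm after deployment | Yes |
| Grams per full chamber set, samples per gram | Core number and weight | Derivable |
| Discordant biopsies | None; nearest are histology, next step and images | No |
| Tissue needed | None; nearest are core number and weight obtained | No |

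The gap is specific to the last two rows.

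**Step 2. Can discordance be derived from what is listed?** It needs the imaging finding, the histology and a rule joining them.
- Histology per lesion is listed.
- Images are collected (sections 5.2 and 6), but no reading, suspicion category or reader is specified.
- The next-step item includes diagnostic surgical biopsy, but the text does not tie it to discordance. It could equally follow an uncertain lesion that is concordant. Repeat needle sampling is not a named option.
- Section 8 tabulates collected variables and derives none of this.

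**Step 3. Can the questionnaires supply it?** They are given when the procedure ends (section 5.2), and section 5.3.1 Primary Endpoints also places the survey score directly after use of the system. Pathology is recorded later (section 5.4). A form completed at that point would normally precede the result it would have to judge.

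**Step 4. Does tissue obtained equal tissue needed?** Only if sampling stopped as soon as the tissue was sufficient. Section 6 sets no special requirement for how biopsies are done, and nothing in the list records the core at which the target was confirmed, or histology by core. The two cannot be equated.

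**Step 5. What a discordance rate could show (illustration only).** Inputs: n = 500 lesions, taking the stated ceiling ("This study will recruit up to 500 females 18 years of age or older") and assuming one lesion per subject; zero discordant lesions, the most favourable result; a comparator rate p0 treated as fixed. No p0 is in the visible text.
- Exact two-sided 95% upper limit with 0 events: U = 1 − 0.025^(1/n).
- n = 500: U = 1 − 0.025^(1/500) = 0.00735, or 0.74%.
- Confirming a 90% reduction needs U < 0.1 × p0, so p0 > 0.735% / 0.1 = 7.35%, about 7.4%.
- If only 250 lesions were collected (assumed): U = 1.465%, so p0 > 14.6%.

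**The case against.** The strongest reply is that the case report forms and questionnaires are not in the text and may already carry a concordance item. That stands as a limit: the gap is shown for the protocol's list and not for the forms. Even so, a quantity the protocol plans to compare with outside sources should be defined in the protocol.

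Second, the documents hint at further review. Section 9.4 mentions an independent physician adjudicator among the site's correspondents, and section 14.1 mentions relevant imaging assessments. Neither says what is assessed, by what rule or when, so neither supplies the item. Procedure images may include images of the cores, but the text does not confirm it or attach a reading to them.

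Third, the study is post-market, observational and descriptive, discordance is not named as an endpoint, and section 5.1.1 says only that the system could provide these gains. This lowers the weight of the point. A descriptive rate still needs a recorded variable.

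A reader might also infer that core weight would be reported with no diagnostic result beside it. The documents do not support that: histology and weight are both listed per lesion, and section 8 tabulates all variables. Only the concordance label is missing.

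**Conclusion.** The point holds for the protocol's own data list. Of the two hypotheses at issue, neither has a direct measure: discordance has no item, definition, assessor or timing, and tissue is recorded only as obtained. The ingredients for a later concordance review are partly collected, so the information is not necessarily lost, but the plan does not produce the rate.

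This rests on reading the protocol text without the forms. It does not depend on any assumed discordance rate.

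A reader might go further and infer from step 5 that 500 subjects cannot confirm the 90% claim. The documents do not support that as a finding. They give no reference rate in the visible text, they plan no formal test, and lesions may outnumber subjects because the inclusion criteria admit women with more than one finding. The figures show only that the added rate should be read as descriptive.

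This is a cheap improvement worth making before data collection, not a flaw that invalidates the study.

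**What to change.** 1. In section 5.3.1 Performance Evaluation, add one per-lesion item, completed by the site when pathology is recorded. Give it a written definition: histology does, or does not, adequately explain the imaging finding that led to biopsy. Add whether repeat sampling was advised. Under section 8, report the per-lesion discordance rate with an exact 95% confidence interval. State whether each comparator source named in section 5.1.1 uses the same definition.

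2. In section 5.1.1, change the tissue hypothesis from tissue needed for accurate diagnosis to tissue obtained. Section 5.3.1 already uses the latter term. Report core number and weight beside the discordance rate, overall and among concordant biopsies.

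If the forms already hold such an item, the change reduces to naming and defining it in the protocol, plus the rewording in step 2.

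Cost: one two-part form item at a moment when pathology is being entered anyway, plus protocol wording; no extra visit and no change to how biopsies are done. Downsides: the site's judgement is unblinded and may vary between sites, and the tissue claim becomes less ambitious.

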5.2 Study Design

Prospective, multi-center, controlled data collection study. This study will include collection of breast imaging from the prior exam leading up to the Brevera Breast Biopsy System Procedure.

Surveys have been created in order to obtain information related to feedback from the clinician(s), patient, and technologist(s). The surveys include questions that relate to the overall feel and aesthetic of the product as well at the overall performance of the Brevera biopsy system. The questionnaires will be given to the clinician(s), patient, and the technologist(s) at the conclusion of the procedure and will be focused for each target group. Once a patient has completed the Brevera procedure, her direct participate in the study is concluded. There are no follow-up visits for this data collection.

The surveys will be administered via paper forms to capture the questionnaire data. The results of the survey questions will be compiled and used to support publications.

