6. STUDY PROCEDURES

The study will collect de-identified case report form data and patient images from biopsy procedures. This will include collection of images from the prior exam leading up to the Brevera Breast Biopsy System Procedure. The biopsy procedures will be done consistent with current clinician direction/standard of care. There are no special requirements under this protocol for how biopsies are performed.

Prior to use of the new Brevera Breast Biopsy System, normal applications training will take place in order to train the users on new features and quality control testing.

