8. STATISTICAL CONSIDERATIONS

The overall sample size for this study is approximately 500 subjects. This sample is expected to be sufficient to provide a basis for providing subjective evidence of clinical performance in a clinical environment. Clinical outcomes data will be collected on all subjects, and survey responses from clinicians, patients, and technologists will be collected and analyzed.

Once all of the data has been collected and cleaned, all variables will be tabulated using descriptive statistics. Continuous variables will be presented as means and standard deviations with 95% confidence intervals, as well as medians and ranges. For categorical variables, relative frequencies and 95% confidence intervals will be provided. The data will be analyzed and compared to previous data collected by Hologic Inc, and to relevant literature.

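### The study is labelled controlled, but it has one group, all having the Brevera procedure, so the five hypothesised reductions rest on external comparison only

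*Combined protocol and SAP*

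**What the plan says.** Section 5.2 opens by calling the study a "Prospective, multi-center, controlled data collection study", and the Design row of the synopsis uses the same words. Section 3 describes it differently: "THIS POST-MARKET, REGISTRY/OBSERVATIONAL STUDY WILL PROVIDE DATA FOR MEASURING DEVICE PERFORMANCE AND OPERATION IN A REAL WORLD SETTING".

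On treatment, section 4.1 says that "the patient would have the Brevera procedure whether or not they choose to participate in this study or not". Section 6 adds: "There are no special requirements under this protocol for how biopsies are performed".

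Section 5.1.1 begins "The hypothesis of this study is that the new breast biopsy system could provide" and lists seven items. Five are reductions: tissue, procedure time, complications, discordant biopsies and marker dislocation. The first reads "50% Reduction in tissue needed for accurate diagnosis". The other two items are tissue yields with no comparison. The same section names the comparators: "The data will be compared to data already collected by Hologic, site aggregate data on the current standard of care, and relevant literature". Section 8 plans descriptive statistics with 95% confidence intervals and then says: "The data will be analyzed and compared to previous data collected by Hologic Inc, and to relevant literature".

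**The concern.** In a design statement, next to hypotheses phrased as reductions, most readers will take the word controlled to mean a comparison group inside the study. The protocol describes no such group.

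What is at stake is what the study may conclude. The survey scores and tissue yields can be described without a control. The five reductions cannot be stated without a comparator, and here every comparator comes from outside the study group. A reader who trusts the label may suppose that differences in patients, operators, period and measurement have been dealt with by design. They have not, and section 8 gives no method for dealing with them in the analysis.

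**Working it through.** The point turns on reading the sections against each other. The planned size of about 500 has no derivation to reproduce (section 8 gives no error rate, power, event rate or standard deviation), and the point does not depend on it.

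**1. Is there a control group anywhere in the protocol?**

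| Place | What it shows |
|---|---|
| Synopsis; 5.2 | Design labelled controlled |
| 3 | Design labelled registry/observational |
| 4.1 | Decliners get the same procedure, so they are not a comparison group |
| 5.3.1 (Performance Evaluation) | Time points are recorded for the Brevera procedure only; no standard-of-care procedure is measured |
| 5.4, Table 1 | One schedule, no arms |
| 5.5.3 | Enrolment is complete at consent; no allocation step follows |
| 6 | Biopsies follow usual practice |
| 8 | One group of about 500; no between-group method |

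No section describes randomisation, a second arm, matching or a within-subject comparison. Section 6.1 speaks of systems in the plural but names no second device. Control subjects enrolled: 0 of about 500.

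**2. Which hypotheses need a comparator?** Of the seven items in 5.1.1, five are reductions. Four carry a percentage (50%, 25%, 50%, 90%); marker dislocation carries none. No reference value is printed beside any of them.

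**3. What could an external comparison show if the device had no effect?** Let E be the rate in the external source and S the rate that standard of care would give in these patients. With no device effect the study observes S, and

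apparent reduction = 1 − S/E.

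The documents give neither E nor S, so these values are assumptions for illustration:

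| E | S | Apparent reduction, no device effect |
|---|---|---|
| 5% | 5% | 1 − 5/5 = 0% |
| 5% | 3.75% | 1 − 3.75/5 = 25% |
| 5% | 2.5% | 1 − 2.5/5 = 50% |

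Only the ratio S/E matters; external rates of 2% or 10% give the same reductions at the same ratios. An apparent 90% reduction would need S/E = 0.10, a much larger mismatch, so the exposure is not equal across the items.

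**4. Does n = 500 protect against this?** No. Take S = 2.5%. The half-width of the 95% interval is 1.96 × √(0.025 × 0.975 / 500) = 0.0137, so the interval runs from about 1.1% to 3.9%. It excludes the assumed external 5% although the device did nothing. The planned interval measures the precision of the Brevera estimate, not the comparability of the external source.

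**5. Is a mismatch plausible from the protocol itself?** For complications, yes. Section 6.2.1 assesses the occurrence of adverse events from consent to discharge, and 5.2 has no follow-up visit. Section 4.2 lists infection, and changes in appearance that depend on healing, among the anticipated events. An external source that followed patients for longer could count more events for that reason alone. Whether any of the planned sources did so is not stated.

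**The case against.** **The phrase may mean controlled collection of data.** The grammar allows it, and 5.2 itself refers to the activity as a data collection. But the protocol never defines the term, and the ordinary reading of a design statement is a control group. The ambiguity is a reason to change the word.

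**The external comparison is disclosed.** It is, in 5.1.1 and again in section 8, so someone who reads the whole protocol can see that the comparators are external. This stands, and it limits the fault to the label and to how the reductions are framed. It does not turn the external sources into a control.

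**The plan is already cautious.** Section 5.1.1 says only that the system could provide the reductions, and section 8 is descriptive and plans no test. This also stands. What is missing is a sentence saying how the differences may be interpreted.

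Three stronger readings are tempting, and the documents do not support them:

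- *The sponsor will publish the reductions as controlled results.* Section 5.2 ties only the survey results to publications, and section 14 leaves publication policy to the study agreement.
- *Patients, operators, period and measurement all differ from the comparators.* This is not shown. If the site aggregates come from the participating sites, operators and case mix may overlap considerably. The supportable statement is that they may differ.
- *All comparison is non-concurrent.* Section 5.1.1 says already collected only of the sponsor's data. The site aggregates are undated and could be concurrent.

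Section 5.1.1 also refers to literature on the last page of the protocol, which was not available for this review. No criticism is made here of how the literature was chosen.

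**Conclusion.** The design label is wrong as written. The synopsis and 5.2 state a property that the design in sections 3 to 8 does not have, and the conflict with section 3 has to be resolved. It bears on five of the seven items in 5.1.1; the two yields and the survey scores are unaffected.

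This is more than a clerical matter, because it decides whether a difference from an outside figure may be presented as an effect of the device. On this design it may not, by itself. That conclusion needs no assumed figures. The rates in the illustration only show how such a difference could arise, and they are not estimates of any real bias.

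**What to change.** 1. **Synopsis (Design) and 5.2:** replace the word controlled with 'single-arm, observational, with external comparison', in line with section 3. Add 'non-concurrent' only if the sponsor confirms that it is true of the site aggregate data.
2. **Section 5.1.1:** express each of the five reductions as a difference from a named external reference. Use the same list of sources in section 8, which at present omits the site aggregates.
3. **Section 8:** add a sentence such as: 'Differences from external references are descriptive and will not by themselves be reported as effects of the device.'

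The cost is an amendment of wording in four places. Sample size, visits and data collection stay as they are. The downside for the sponsor is a more modest claim.
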